5.6 SAFETY ANALYSES

Unless specified otherwise, the safety analyses described below will be conducted for the safety-evaluable population (see Section 4), with patients grouped according to whether or not any atezolizumab treatment was received (i.e., patients who received any dose of atezolizumab will be included in the atezolizumab arm).

5.6.1 Extent of Exposure

Summaries of exposure to study treatment will include treatment duration, number of doses, and dose intensity.

5.6.2 Adverse Events

Verbatim description of adverse events will be summarized by mapped thesaurus term using Medical Dictionary for Regulatory Activities (MedDRA), and graded according to National Cancer Institute Common Terminology Criteria for Adverse Events (NCI CTCAE) v4.0. All adverse events occurring during or after the first study-drug dose until the clinical cutoff date will be summarized by treatment arm and NCI CTCAE grade. In addition, serious adverse events, Grade ≥ 3 adverse events, adverse events of special interest, adverse events leading to treatment discontinuation, and adverse events leading to treatment interruption will be summarized. Multiple occurrences of the same event will be counted once at the maximum grade.

Selected laboratory data will be summarized by treatment arm. Changes in selected vital signs will be summarized by treatment arm.

Deaths and causes of death reported during the study treatment period and those reported during the follow-up period after treatment completion/discontinuation will be summarized by treatment arm.

5.7 OTHER ANALYSES

5.7.1 Summaries of Conduct of Study

Major protocol deviations, including major deviations of inclusion and/or exclusion criteria, will be summarized by treatment arm.

5.7.2 Summaries of Treatment Group Comparability

Demographic characteristics (e.g., age, sex, race/ethnicity), stratification factors (disease stage [T2/T3a vs. T3b/c/T4/N+ vs. patients with resected synchronous/metachronous metastasis], geographic region [North America (excluding Mexico) vs. rest of world], PD-L1 expression [IC0 vs. IC1/2/3]), and baseline disease characteristics (e.g., Eastern Cooperative Oncology Group (ECOG) performance status) will be summarized by treatment arm for the ITT population.

Continuous variables will be summarized using means, standard deviations, medians, and ranges. Categorical variables will be summarized by frequencies and percentages. Baseline measurements are the last available data obtained prior to the patient receiving the first dose of study treatment.

5.7.3 Pharmacokinetic Analyses

Pharmacokinetic (PK) analyses will be performed in the pharmacokinetic-evaluable population (see Section 4). Atezolizumab serum concentration data (minimum [C_{min}] and maximum [C_{max}]) will be reported and summarized (e.g., mean, SD, coefficient of variation, median, range, geometric mean, geometric mean coefficient of variation) for each cycle where collected as appropriate.

Additional PK analyses will be conducted as appropriate based on the available data.

5.7.4 Immunogenicity Analyses

The immunogenicity analysis population will consist of all patients with at least one ADA assessment for atezolizumab. The post-baseline ADA-evaluable population will be grouped according to treatment received (see Section 4). The numbers and proportions of ADA-positive patients and ADA-negative patients at baseline (baseline prevalence) and after drug administration (post-baseline incidence) will be summarized by treatment group. When considering post-baseline incidence, patients are considered to be ADA positive if they are ADA negative or with missing data at baseline but develop an ADA response following study treatment administration (treatment-induced ADA response), or if they are ADA positive at baseline and the titer of one or more post-baseline samples is at least 4-fold greater (i.e., ≥ 0.60 titer units) than the titer of the baseline sample (treatment-enhanced ADA response). Patients are considered to be ADA negative if

they are ADA negative or with missing data at baseline and all post-baseline samples are negative, or if they are ADA positive at baseline but do not have any post-baseline samples with a titer that is at least 0.60 titer units greater than the titer of the baseline sample (treatment unaffected).

The relationship between ADA status and safety, efficacy, and PK endpoints may be analyzed and reported descriptively via subgroup analyses.

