• Secondary Efficacy Objective (cont.)	
	
 • 1-, 2-, and 3-year IRF-assessed DFS rate, defined as the probability of patients being alive and free of recurrence assessed by IRF at Year 1, 2, and 3 after randomization
Safety Objective	

 • To evaluate the safety and tolerability of atezolizumab in the adjuvant setting 	
 • Incidence, nature, and severity of adverse events graded according to NCI CTCAE v4.0 • Changes in vital signs and clinical laboratory results
Pharmacokinetic Objective	

 • To characterize the PK profile of atezolizumab 	
 • Serum concentration of atezolizumab at specified timepoints
Immunogenicity Objectives	

 • To evaluate the immune response to atezolizumab • To explore the potential relationship of the immunogenic response 	
 • Prevalence of anti-drug antibodies (ADAs) to atezolizumab at baseline and incidence of ADAs to atezolizumab after treatment • Relationship between ADA status and PK (i.e., minimum serum concentration), safety, and efficacy endpoints
Exploratory Objectives	

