3.1.1 Study Treatment

Patients in both treatment arms will receive up to 1 year of treatment with either atezolizumab or placebo. Treatment will be administered intravenously on Day 1 of each 21-day cycle. Treatment will be discontinued in the event of disease recurrence, unacceptable toxicity, consent withdrawal, or study termination by the Sponsor.

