Appendix 2 Schedule of Pharmacokinetic, Immunogenicity, and Biomarker Samples

Visit	Timepoint	Sample Type
Cycle 1, Day 1	Pre-dose	Serum atezolizumab ADA Serum atezolizumab pharmacokinetics Plasma PD biomarker Serum PD Biomarker Whole blood PBMC
	30 min (\pm 10 min) (after the end of infusion)	Serum atezolizumab pharmacokinetics
Cycles 2 and 4, Day 1	Pre-dose	Plasma PD biomarker Serum PD biomarker
Cycles 2, 3, and 4, Day 1	Pre-dose	Serum atezolizumab ADA Serum atezolizumab pharmacokinetics
Cycle 8, Day 1	Pre-dose	Serum atezolizumab ADA Serum atezolizumab pharmacokinetics
Treatment discontinuation visit ^a	At visit	Serum atezolizumab ADA Serum atezolizumab pharmacokinetics
	At visit	Plasma PD biomarker Serum PD biomarker
At disease recurrence ^{b, c}	At visit ^d	Plasma PD biomarker Serum PD biomarker

ADA = anti-drug antibody; PBMC = peripheral blood mononuclear cell;
PD = pharmacodynamic.

- ^a Treatment discontinuation visit occurs within 30 days after last dose of study treatment and applies to all patients who discontinue study treatment (regardless of the reason).
- ^b If a patient discontinues the study due to disease recurrence, it is acceptable to collect PD blood at the visit at which tumor assessment shows disease recurrence only, and waive collection at the treatment discontinuation visit.
- ^c Disease recurrence blood sample collection should occur at the same time as disease recurrence tissue biopsy sample collection. Disease recurrence blood sample should still be collected even if the Medical Monitor waives the requirement for tissue biopsy sample.
- ^d It is acceptable to collect the disease recurrence samples at either investigator-assessed recurrence or IRF-assessed disease recurrence. The disease recurrence samples must be collected within 2 weeks after disease recurrence has been confirmed.

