4. ANALYSIS SETS

The following populations are defined:

Population	Definition
ITT	All randomized patients regardless of whether the assigned study treatment was received.
Safety-evaluable	All randomized patients who received any amount of study treatment (i.e., atezolizumab or placebo), regardless of whether a full or partial dose was received. Specifically, for patients randomized to the placebo arm, if atezolizumab was received by mistake, patients will be grouped under the atezolizumab arm in the safety analyses.
PRO-Evaluable	All randomized patients with a non-missing baseline PRO assessment and at least one post-baseline assessment. The PRO-evaluable population will be defined for each questionnaire (i.e., the FKSI-19 evaluable population and the EQ-5D-5L evaluable population).
Immunogenicity Analysis	All randomized patients with at least one ADA assessment for atezolizumab
Post-baseline ADA-Evaluable	All randomized patients who received at least one dose of atezolizumab and with at least one postdose ADA assessment
Pharmacokinetic-Evaluable	All randomized patients who received any dose of study treatment and who have at least one measurable post-baseline PK sample available

ADA = anti-drug antibody; EQ-5D-5L = EuroQoL 5-Dimension, 5-level version;
FKSI-19 = Functional Assessment of Cancer Therapy Kidney Symptom Index 19;
ITT = intent-to-treat; PK=pharmacokinetic; PRO = patient reported outcomes.

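### Efficacy by post-baseline ADA status has no time window while DFS and OS run from randomization, so the comparison can tilt toward ADA-positive patients if ADA appears late

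*SAP*

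**What the plan says.** Protocol Section 2 (Table 4) lists this endpoint under the objective of exploring the immunogenic response: "Relationship between ADA status and PK (i.e., minimum serum concentration), safety, and efficacy endpoints". The SAP's Table 1 repeats it. The method, in SAP 5.7.4 and almost identically in Protocol 6.7, is optional and descriptive: "The relationship between ADA status and safety, efficacy, and PK endpoints may be analyzed and reported descriptively via subgroup analyses".

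The elements that determine how the subgroups form are these:

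- **ADA-positive after baseline (SAP 5.7.4).** Patients count as positive "if they are ADA negative or with missing data at baseline but develop an ADA response following study treatment administration (treatment-induced ADA response". Patients already positive at baseline need a 4-fold titer rise. Neither rule has a time limit.
- **ADA-negative (SAP 5.7.4).** For patients negative or missing at baseline, the condition is that "all post-baseline samples are negative", however few samples there are.
- **Evaluable set (SAP Section 4).** "All randomized patients who received at least one dose of atezolizumab and with at least one postdose ADA assessment". One post-dose sample is therefore enough.
- **Sampling (Protocol Appendix 2).** Pre-dose at "Cycles 2, 3, and 4, Day 1", again at Cycle 8 Day 1, and finally at the discontinuation visit: "Treatment discontinuation visit occurs within 30 days after last dose of study treatment". That last sample is due whatever the reason for stopping.
- **Stopping (Protocol 3.1.1).** "Treatment will be discontinued in the event of disease recurrence". Protocol 4.6.2 ties this to recurrence determined by the IRF, whereas 3.1.1 names no assessor. The two should be reconciled, but the difference affects when sampling stops, not the argument here.
- **Time origin (SAP 5.3.1 and 5.4.1).** DFS and OS both start at randomization.

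Neither document names a landmark, a time-dependent ADA covariate, or a fixed early time for classifying ADA status.

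**The concern.** ADA status after baseline is learned during follow-up and is partly shaped by the outcome. Recurrence stops treatment. After one discontinuation-visit sample, it also stops the search for ADA. Conversely, a patient first found positive at the end of the treatment year must have stayed on treatment until then. Counting that waiting time from randomization credits event-free time to the ADA-positive group. This is immortal-time bias, and it always runs in favour of ADA-positive patients.

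That direction matters because it reassures. Protocol 1.3.2.3 already reports no clinically relevant relationship between ADA status and efficacy to date, and also that ADA altered pharmacokinetics in some patients at lower doses. An analysis leaning toward ADA-positive patients could offset a real loss of efficacy and appear to confirm the absence of a relationship.

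**Working it through.** **Step 1. Check the planning inputs.** The documents give no figure for the ADA analysis, so the DFS event count is the one to reproduce. With HR 0.70, two-sided alpha 0.05 and 90% power, the Schoenfeld formula gives 4 × (1.960 + 1.282)² / (ln 0.70)² = 42.03 / 0.1272 = 331 events after rounding up. With HR = 47/67 = 0.7015 it gives 335. The plan states 334, so its medians are sound inputs.

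**Step 2. How many patients have a shortened window?** Under exponential DFS with the planned atezolizumab median of 67 months, P(event by t) = 1 − 2^(−t/67).

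- Week 9 (2.07 months): 2.1%
- Month 3: 3.1%
- Week 21: 4.9%
- Month 12: 11.7% (16.2% if the median is 47 months)

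Cycles 2, 3, 4 and 8 fall at weeks 3, 6, 9 and 21. Cycle 16 starts at week 15 × 3 = 45, so a completer's discontinuation sample falls by about week 49. Three post-dose samples precede the first scheduled scan at month 3. After week 21 only the discontinuation sample remains.

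**Step 3. Simulate with no ADA effect.** From the documents: median DFS 67 months, scans every 3 months for 3 years and then every 6, the Appendix 2 samples including the discontinuation visit, treatment stopped at detected recurrence, and follow-up of 34-67 months. Assumed: 10%, 30% or 50% of patients convert; four onset patterns; no dropout; for OS, exponential survival after recurrence with a median of about 52 months, chosen to give the planned 143-month median OS. The comparison is a Cox model of ever-positive versus never-positive, from randomization.

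| ADA onset (assumed) | DFS HR at 10 / 30 / 50% | OS HR at 10 / 30 / 50% | DFS HR, week-9 landmark |
|---|---|---|---|
| All by week 9 | 1.00 / 1.00 / 1.00 | about 1.00 | 1.00 |
| Uniform to week 21 | 0.97 / 0.96 / 0.94 | 0.95 / 0.95 / 0.93 | 1.00-1.01 |
| Median 9 weeks, tail to week 49 | 0.96 / 0.95 / 0.93 | 0.95 / 0.93 / 0.90 | 1.00-1.01 |
| Uniform to week 49 | 0.88 / 0.86 / 0.81 | 0.85 / 0.82 / 0.77 | 0.99-1.01 |

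With a 47-month median and 30% converting, the last three rows give DFS HRs of about 0.96, 0.94 and 0.85. Other settings (15% a year stopping for other reasons, 20-40% converting, medians of 47 or 67 months) give 0.94-0.98 for mainly early onset and 0.82-0.90 for spread onset. The week-9 landmark gives 0.98-1.03 throughout.

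**Step 4. Compare with sampling error.** Half of 764 is 382 atezolizumab patients. Averaging over uniform follow-up of 34-67 months, the event fraction is 1 − (2^(−34/67) − 2^(−1)) / (33 × ln 2 / 67) = 1 − (0.7035 − 0.5) / 0.3414 = 0.404. That is about 154 events, say 150. With 30% ADA-positive, the SE of log HR is 1 / √(150 × 0.3 × 0.7) = 0.178, so a 95% interval around 1.0 runs from about 0.71 to 1.42. A spurious HR of 0.95 is 0.051 / 0.178 = 0.29 SE. One of 0.86 is 0.151 / 0.178 = 0.85 SE.

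**The case against.** The strongest reply is that the plan does not commit to the biased analysis. SAP 5.7.4 does not say which ADA status defines the efficacy subgroups. Its positive and negative rules are introduced for reporting incidence, and baseline status, also summarized there, would carry no such bias. This stands as a limit. Post-baseline status is an inference, supported by the objective's reference to the immunogenic response, and the silence itself needs correcting.

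Second, sampling is front-loaded and a patient who recurs still gives a discontinuation sample. Someone recurring at month 4 has the Cycle 2, 3 and 4 samples plus that one, only one fewer than a completer. This also stands, and it is why the bias vanishes when ADA appears by week 9.

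Third, Step 4 shows that the bias is within sampling error, and the analysis is exploratory. That limits the consequence. It does not justify keeping a method whose error has a known direction when an equally simple one avoids it.

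A reader might go further and infer that ADA-positive patients will look better whatever the onset pattern, with an HR in the low 0.8s. The documents do not support this. Uniform onset over the year puts 1 − 9/49 = 82% of conversions after week 9, and nothing in either document says so. Nor does either document plan a claim that ADA has no effect on efficacy, or specify a comparison of ADA-positive patients with placebo. Protocol 4.2.2 says control-arm samples are assayed only on request.

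**Conclusion.** The point holds conditionally. If post-baseline ADA status defines the subgroups and time runs from randomization, the comparison leans toward ADA-positive patients, and nothing in the plan corrects for it. With no true effect, the DFS hazard ratio ranges from about 1.0 (onset by week 9), through 0.93-0.98 (intermediate onset), to 0.81-0.90 (onset spread over the year). The size rests on assumed ADA incidence and onset, exponential event times and no dropout. The direction does not depend on the assumed incidence or median.

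The DFS test and the formal OS test are untouched, because the ADA analysis sits outside the testing hierarchy.

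It might seem to follow that the safety summaries by ADA status need the same landmark, since longer treatment brings both more ADA samples and more adverse events. That step should not be taken. It would discard events from Cycles 1-3, including infusion-related reactions and hypersensitivity, which Protocol 5.2.3 lists as adverse events of special interest.

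**What to change.** In SAP 5.7.4 and Protocol 6.7:

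1. State whether the efficacy subgroups use baseline or post-baseline ADA status.
2. For DFS and OS by post-baseline status, specify a landmark at Cycle 4 Day 1. Classify status from samples up to then, include only patients event-free at that point, and count time from it. Any placebo comparator should be event-free at the same landmark. ADA as a time-dependent covariate is an acceptable alternative.
3. Report the number of ADA samples per patient in each ADA group.
4. Leave the safety summaries without a landmark.

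The cost is SAP wording and reprogramming of descriptive tables, with no new samples. The landmark version has two drawbacks: patients who convert after Cycle 4 count as ADA-negative, and about 2% of atezolizumab patients, those with an earlier event, are left out.

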5.7.5 Patient-Reported Outcomes Analyses

5.7.5.1 Functional Assessment of Cancer Therapy Kidney Symptom Index 19 (FKSI-19)

PRO analyses will be performed in the FKSI-19-evaluable population (see Section 4), unless otherwise specified.

Compliance rates for the FKSI-19 will be calculated as the number of patients who completed the assessment divided by the number of patients expected to complete the assessment at each timepoint for each treatment arm in the ITT population. Reasons for missing assessments, if available, will be summarized with frequencies and percentages.

Instruments will be scored per their user manual; subscales with less than 50% of the items completed will be considered missing. Missing data will not be imputed.

The FKSI-19 (version 2) can be scored as a Total scale and as five subscales:

- Total scale (Total, 19 items; score range of 0-76)
- Physical disease-related symptoms (DRS-P, 12 items; score range of 0-48)
- Emotional disease-related symptoms (DRS-E, 1 item; score range of 0-4)
- Treatment side effects (TSE, 3 items; scored individually 0-4)
- Function/well-being (FWB, 3 items; score range of 0-12)
- Disease-related symptoms (DRS, 9 items; score range of 0-36)

Higher scores indicate lower symptom or disease burden. The scoring of the FKSI-19 and its subscales will be done in accordance with FKSI-19 Scoring guidelines (Version 2; [FKSI-19](#)).

Descriptive analyses will include summary statistics (mean, SD, median, interquartile range [IQR], minimum, maximum) of each score and score changes from baseline at each assessment timepoint by treatment arm. Descriptive summaries will be reported for each FKSI-19 subscale (DRS-P, DRS-E, TSE, FWB, DRS) as well as the FKSI-19 Total

scale. Graphs of mean scores and/or score changes from baseline along with two-sided 95% CIs may be presented.

Time to confirmed deterioration (TTCD) analyses will be performed for each FKSI-19 subscale and Total scale in the ITT population. TTCD is defined as the time from the date of randomization to the date of a clinically meaningful score change from baseline that is held for at least two consecutive timepoints, or followed by death within 6 weeks from the last PRO assessment. Patients who do not experience a confirmed deterioration event at the time of clinical data cutoff will be censored at the last timepoint when they completed an assessment. Patients with no baseline or no post-baseline assessment will be censored at the randomization date. TTCD using the FKSI-19 scale will be analyzed similarly to the analysis of investigator-assessed DFS.

A clinically meaningful score change is defined as a 3-point or more score decrease on the FKSI-19 Total scale and DRS subscale (Cella et al. 2007, Yost and Eton 2005); a 4 point or more score decrease on the DRS-P subscale; and a 1-point or more score decrease on the DRS-E, TSE, and FWB subscales (Cella et al. 2018, Yost and Eton 2005).

Overall AE burden, as measured by the FKSI-19 GP5 item, will be summarized descriptively (numbers and proportions of responses) at each assessment timepoint in the safety-evaluable population. The distribution of responses and/or change from baseline will be illustrated by stacked bar charts for each arm.

To assess the consistency of the FKSI-19 results, the TTCD analysis (as defined above) will be performed on the subgroups defined by demographic and baseline characteristics. The outputs will include unstratified HRs estimated from the Cox proportional hazards model with associated 95% confidence intervals and, Kaplan-Meier estimates of the median will be produced separately for each level of the subgroup.

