
 • To assess predictive, prognostic, and pharmacodynamic exploratory biomarkers in archival and/or fresh tumor tissue and blood and their association with disease recurrence and overall survival • To document patients' perspective regarding treatment tolerability and health-related quality of life • To measure health status for health economic modeling • To evaluate the efficacy of adjuvant treatment with atezolizumab among patients with tumor Fuhrman Grade 4 or sarcomatoid histology (defined by investigator-assessed conventional histopathology) 	
 • Tumor and circulating biomarkers (including, but not limited to PD-L1, PD-1, prevalence of immune subsets, circulating factors, genomic mutations, gene expression, gene expression signatures of tumor and immune biology, and molecular subtypes), as defined by IHC or qRT-PCR, NGS, and/or other methods will be correlated with efficacy measures. • The Functional Assessment of Cancer Therapy Kidney Symptom Index 19 (FKSI-19) • EQ-5D-5L questionnaire as a measure of patient reported health status to derive utilities • Investigator-assessed DFS in patients with tumor Fuhrman Grade 4 or sarcomatoid histology (defined by the investigator-assessed conventional histopathology).

ADA= anti-drug antibody; DFS=disease free-survival; *EFS = event free survival*, EQ-5D-5L= EuroQoL 5-Dimension, 5-level version; IC=tumor-infiltrating immune cell; IHC=immunohistochemistry; IRF=Independent Review Facility; NCI CTCAE v4.0=National Cancer Institute Common Terminology Criteria for Adverse Events Version 4.0; NGS=next generation sequencing; PD-1=programmed death-1; PD-L1=programmed death ligand-1; PK=pharmacokinetic; qRT-PCR=quantitative reverse transcriptase=polymerase chain reaction; RCC=renal cell carcinoma

**PD-L1 IC0 is defined as <1% and IC1/2/3 is defined as ≥1% of tumor-infiltrating immune cells (IC) expressing PD-L1 as assessed by immunohistochemistry using SP142 assay.*

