3.3.6 Rationale for Efficacy Endpoints

The treatment benefit in this study will be measured using DFS as the primary efficacy endpoint and OS, DFS in IC1/2/3 patients, distant metastasis-free survival (DMFS), 1-, 2-, and 3-year DFS, and disease specific-survival (DSS) as secondary efficacy endpoints.

Improvement in DFS and the ability to delay surgery or the initiation of metastatic treatment such as tyrosine kinase inhibitors ([TKIs]; e.g., sunitinib, pazopanib) represents clinically meaningful benefit to patients with RCC. Given that the current

standard regimens for metastatic disease, such as TKIs, are associated with significant chronic toxicities such as fatigue, diarrhea, mucositis, and hand–foot syndrome (Motzer et al. 2014), improvement in DFS delays the initiation of these adverse events associated with first-line therapy and therefore reflects direct benefit to patients. Also, interpretation of DFS is not confounded by the use of subsequent therapies. Given the availability and ongoing development of multiple agents in the relapsed and metastatic settings, interpretation of OS may be confounded by the use of subsequent therapies in this patient population. Current studies in adjuvant RCC (S–TRAC, SORCE, PROTECT, ATLAS, EVEREST) employ a DFS endpoint.

The primary efficacy objective endpoint of investigator-assessed DFS is considered an adequate clinical endpoint for an adjuvant clinical trial in RCC that better approximates treatment benefit in real world clinical practice and has been employed in several pivotal Phase III adjuvant RCC studies (Haas et al. 2016; Choueiri et al. 2021). Moreover, investigator-assessed DFS has been accepted as a surrogate endpoint for OS to support drug approval in the adjuvant setting in other malignancies, including NSCLC (Wu et al. 2021), breast cancer (Masuda et al. 2017), urothelial cancer (Bajorin et al. 2021), and colon cancer (Andre et al. 2004). Given the blinded trial design, investigator assessment is acceptable for the determination of recurrence in this setting and better approximates clinical practice (McKay et al. 2021).

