4.5.10 Post-Treatment Assessments

Refer to Section 4.5.5 and [Appendix 1](#) for details of assessments of surveillance of RCC recurrence, including assessments following study treatment completion. After discontinuation of the study treatment, PRO questionnaires will be administered over the phone or at the site at end of treatment visit, the post-treatment visit, any visit for assessment of RCC recurrence, and at two timepoints after disease recurrence during survival follow-up. Post-study treatment follow-up visits for tumor recurrence

surveillance should also include monitoring for potential late serious adverse events and adverse events of special interest.

Following completion of the last treatment cycle, patients will return for a treatment discontinuation visit within 30 days of the last study dose and a post-treatment visit 3 months after the last dose.

Survival follow-up information will be collected via telephone calls, patient medical records, and/or clinic visits approximately every 3 months until death, loss to follow-up, consent withdrawal, or study termination by the Sponsor. All patients (irrespective of the arm to which they are randomized) will be followed for survival and new anti-cancer therapy information (including targeted therapies and immunotherapies) and subsequent progressions, unless the patient requests to be withdrawn from follow-up; this request must be documented in the source documents and signed by the investigator. If a patient withdraws from *the study*, study staff may use a public information source (e.g., county records) to obtain information about survival status.

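### The FKSI-19 side-effect deterioration analysis does not stop at new anti-cancer therapy, so it can mix next-line toxicity with tolerability of the study drug

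*SAP*

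**What the plan says.** SAP 5.7.5.1 sets the scope: "Time to confirmed deterioration (TTCD) analyses will be performed for each FKSI-19 subscale and Total scale in the ITT population". For TSE, a fall of one point is an event if it is "held for at least two consecutive timepoints", or if death follows within 6 weeks of the last questionnaire. Patients without an event "will be censored at the last timepoint when they completed an assessment"; those lacking baseline or post-baseline data are censored at randomization. Protocol 6.9.1 has the same censoring. Neither document mentions recurrence or new therapy in this rule.

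Study drug lasts at most one year. Questionnaires continue at the end-of-treatment and post-treatment visits, at any recurrence-assessment visit "and at two timepoints after disease recurrence during survival follow-up" (Protocol 4.5.10; likewise 4.5.8). SAP 1.2.1 keeps tumour assessments going after new anti-cancer therapy until the IRF calls recurrence, so questionnaires can also continue past an investigator-called recurrence.

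The objective is the patient's "perspective regarding treatment tolerability and health-related quality of life" (Protocol Table 4). For the single item GP5, "Overall AE burden, as measured by the FKSI-19 GP5 item, will be summarized descriptively", at each assessment timepoint in the safety-evaluable population.

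**The concern.** The three TSE items ask about nausea, diarrhea and bother from side effects of treatment (Protocol Appendix 5). The last of these does not say which treatment. After recurrence the patient may be answering about a different drug. Protocol 3.3.6 says that the standard metastatic regimens "are associated with significant chronic toxicities such as fatigue, diarrhea, mucositis", and argues that better DFS postpones those effects. By the protocol's own reasoning, an arm that delays recurrence should then have fewer or later TSE events through efficacy alone.

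The rest of the plan treats this differently. Adverse event reporting ends at new systemic anti-cancer therapy, or earlier at 30 days after the last dose (90 days for serious events and events of special interest; Protocol 5.3.1). SAP 5.4.1.1 allows an OS sensitivity analysis for later immunotherapy in the placebo arm. There is no counterpart for TSE. At stake is a tolerability statement: Protocol 3.3.9 wants the questionnaire to show whether a survival gain comes with harmful effects, and this analysis could understate them in exactly that case.

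**Working it through.** **Inputs.** From SAP 3.2: medians 47 and 67 months, HR 0.70, two-sided 0.05, 90% power, 334 events, 764 patients (382 per arm), 33 months' accrual with an 8-month ramp-up, 5% loss over 24 months, analysis at Month 67. The FKSI-19 section gives no power or event figures.

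**1. The plan's own figure.** Events = 4(z₀.₉₇₅ + z₀.₉₀)² / (ln HR)² = 4(1.960 + 1.282)² / (ln 0.70)² = 331; with HR = 47/67 it is 335. Power with 334 events is 0.903 and 0.900 respectively. The stated 334 is reproduced, so the medians can be used for the next steps.

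**2. Share with a DFS event by time t**, exponential: 1 − 0.5^(t/median).
- Month 12: 16.2% placebo, 11.7% atezolizumab.
- Month 36: 41.2% and 31.1%, or 157 and 119 of 382, a gap of 38.

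With at most a year of study drug, most of these events fall after treatment has ended.

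**3. By Month 67**, with the stated accrual (with or without the ramp) and dropout: about 185–190 events on placebo and 143–147 on atezolizumab. The total is 328–336, against 334 planned. That is 42–43 more on placebo.

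**4. From DFS events to TSE events.** The 38 is not a count of extra TSE events. It includes deaths, not every recurrence leads to systemic therapy, and TTCD counts only a first event. The documents give none of these shares. Assume that 20–40% of patients have already deteriorated on treatment and that 20–60% of recurrent patients deteriorate afterwards. Then 38 becomes 38 × 0.6 × 0.2 ≈ 5 to 38 × 0.8 × 0.6 ≈ 18 extra placebo events, beside 382 × 0.2 = 76 to 382 × 0.4 = 153 on-treatment placebo events.

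**5. Effect on the hazard ratio.** A simulation (1,500 replicates) used the design inputs and the assumed ranges from step 4. It treated every DFS event as a recurrence, placed post-recurrence deterioration 3 months later and ended questionnaires 6 months after recurrence. TSE hazard ratios, atezolizumab against placebo:

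| True on-treatment HR | Placebo deteriorating on treatment | All follow-up, with 20% / 40% / 60% deteriorating after recurrence | Censored at recurrence |
|---|---|---|---|
| 1.00 | 20% | 0.93 / 0.87 / 0.84 | 1.00 |
| 1.00 | 40% | 0.97 / 0.94 / 0.91 | 1.00 |
| 1.30 | 20% | 1.14 / 1.04 / 0.98 | 1.31 |
| 1.30 | 40% | 1.23 / 1.17 / 1.11 | 1.30 |

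With no post-recurrence deterioration, the all-follow-up analysis gives 1.02 and 1.32–1.33, so the shift comes from the post-recurrence events. The simulation censors at recurrence. Censoring at new therapy would act the same way only in so far as the later toxicity comes from that therapy.

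**The case against.** The strongest reply is that all-follow-up analysis was a choice. The protocol's summary of changes says TTCD was added so that all captured FKSI-19 data could be analysed, and the objective speaks of treatment tolerability without restricting it to study treatment. Read as a treatment-policy question, delayed exposure to next-line toxicity is a real benefit of the assigned arm. This stands as a reason to keep the planned analysis. It does not make the result a measure of the study drug's side effects.

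Second, on-treatment evidence is already planned: TSE scores and changes by visit and arm, GP5 by visit, and adverse events within a closed reporting window. This stands too, and limits the harm. TSE TTCD is one of six TTCD analyses of an exploratory endpoint outside the alpha hierarchy.

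Third, censoring has its own bias. Starting new therapy is informative and may differ by arm. A window tied to the last dose would shorten follow-up for patients who stop early for toxicity, and a fall first seen at the last visit in the window could never be confirmed. Delayed immune-mediated effects might be lost that way. These points rule out replacing the planned analysis and shape the proposal below.

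**Conclusion.** The gap is real but minor, and it is confined to TSE TTCD. As written, a confirmed TSE fall after recurrence counts for the randomised arm whatever drug caused it. The two post-recurrence questionnaires can confirm one by themselves if both fall during next-line therapy; their timing is not specified. Under the design medians and the assumed deterioration rates, a true hazard ratio of 1.00 reads 0.84–0.97 and a true 1.30 reads 0.98–1.23.

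Three stronger readings are not supported:
- A reader might infer that placebo is penalised regardless. The tilt depends on a DFS benefit and disappears if recurrence does not differ between arms.
- A reader might infer that worse tolerability would turn into apparent superiority. With a true 1.30 the result is mostly attenuation. Only the most extreme combination falls just below 1, and the rates are not from the documents.
- A reader might infer that GP5 accumulates next-line toxicity in the same way. It is summarised descriptively visit by visit, and treatment is discontinued on recurrence, so the on-treatment displays largely stand. Only later visits mix drugs.

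The month-36 shares of 41% and 31% are upper bounds on patients who could start next-line drugs. DFS and OS inference is unaffected.

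**What to change.** In SAP 5.7.5.1, before unblinding:
- Keep the all-follow-up TSE TTCD, labelled as including the effects of subsequent therapy.
- Pre-specify beside it a TSE TTCD censored at the last assessment before the start of new systemic anti-cancer therapy. Let a fall first seen before that start, including at the post-treatment visit, be confirmed by the next assessment if new therapy has still not begun.
- Base any statement about study-drug tolerability on this second analysis and on the on-treatment TSE and GP5 summaries.
- Show post-treatment GP5 responses separately by whether new therapy had started.
- Leave the other FKSI-19 scales as planned.

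The cost is SAP wording and one derived flag; new anti-cancer therapy is already followed up under Protocol 4.5.10. The second analysis will have fewer events and possibly informative censoring, which is why both are reported.
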